Study Protocol and Statistical Analysis Plan

Study title: The Effects of Wild Blueberries on Depressive Symptoms in Young Adults

Acronym: BluMood

Date: 07 April 2022

1. Sample Size Calculation

A mixed-design ANOVA carried out on data from a previous study in adolescents demonstrated a medium effect size (partial $\eta^2 = 0.04$) of a four-week blueberry intervention on depressive symptoms (Fisk, Khalid, Reynolds, & Williams, 2020). An *a priori* power analysis in G*Power with this effect size indicated that a sample of 60 participants would be necessary to achieve a power level of 0.80 at a significance level of 0.05.

2. Recruitment and Screening

Participants will be recruited using opportunity sampling. The study will be advertised through email distribution and with posters across the University of Reading. Before interested participants are enrolled in the trial, we will invite them to the lab for a screening session to determine if they meet the eligibility criteria and give them an opportunity to become familiar with the cognitive task battery so as to reduce the influence of practice effects. Participants will be compensated with £120 (\$156) for completing all phases of the study.

3. Randomization and Blinding Process

A researcher not involved in recruitment or data collection will use blocked randomization with random permuted blocks of two and four individuals to form the allocation list for the two comparison groups. The allocation sequence will be generated using the online randomization tool Sealed Envelope (v1.19.1) and will be concealed to the researchers enrolling and assessing participants. The interventions for chronic consumption will be distributed to participants in opaque, sealed sachets whereas on testing days the intervention drinks will be administered in opaque shaker bottles prepared by research personnel not involved in the conduct of the trial. Thus, both participants and investigators will be blinded to the treatment assignment throughout the study.

4. Testing Protocol

Visit 1

09:00 – participants consume a standard breakfast of oat porridge after an overnight fast

09:40 – participants complete cognitive task + PANAS-X

10:00 – blood sample taken

10:10 – participants consume the drink they have been allocated to (blueberry or placebo)

11:10 – participants complete a battery of questionnaires (e.g. BDI-II, PHQ-9)

11:25 – participants have their heart rate variability measured

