12:10 – participants complete cognitive task + PANAS-X

12:25 – participants are given a bag with 41 sachets for the chronic phase of the study

Visit 2

09:00 – participants consume a standard breakfast of oat porridge after an overnight fast

09:30 – participants complete a battery of questionnaires (e.g. BDI-II, PHQ-9)

09:50 – participants have their heart rate variability measured

10:00 – participants complete cognitive tasks + PANAS-X

10:25 – blood sample taken

5. Statistical Analysis Plan

The outcomes will be analyzed using ANCOVAs adjusted for baseline values, sex, and habitual fruit and vegetable consumption as long as the assumptions for conducting the analysis are met.

References

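### For the depression questionnaires and heart rate variability, the only listed Visit 1 value follows the allocated drink, so the baseline covariate in the ANCOVA is post-treatment

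*Combined protocol and SAP*

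**What the plan says.** Section 5 is a single sentence. Its main clause reads "The outcomes will be analyzed using ANCOVAs adjusted for baseline values, sex, and habitual fruit and vegetable consumption". A proviso then makes this conditional: "as long as the assumptions for conducting the analysis are met". The sentence ties baseline to no visit or clock time.

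Section 4 gives the order of events at Visit 1:

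- Cognition and mood come first: "09:40 – participants complete cognitive task + PANAS-X".
- Blood is next, still ahead of treatment: "10:00 – blood sample taken".
- Treatment then begins: "10:10 – participants consume the drink they have been allocated to (blueberry or placebo".
- The depression measures come an hour later: "11:10 – participants complete a battery of questionnaires (e.g. BDI-II, PHQ-9".
- The cardiac measure is the next entry: "11:25 – participants have their heart rate variability measured".

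At Visit 2 the corresponding questionnaire entry is "09:30 – participants complete a battery of questionnaires (e.g. BDI-II, PHQ-9", with heart rate variability at 09:50. The Visit 2 list contains no drink. Section 2 describes screening only as an eligibility check and practice on the cognitive tasks. It mentions no questionnaire score or heart rate variability recording.

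**The concern.** The ANCOVA group coefficient equals the treatment effect at Visit 2 only if treatment has not changed the covariate. Randomisation guarantees that for anything measured before the first drink. It gives no such guarantee for a value taken an hour afterwards. If the drink improves mood or heart rate variability within that hour, adjustment removes part of the effect the trial wants to measure. With no effect at Visit 2, the same adjustment can make the active arm look worse.

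The affected questionnaires carry depressive symptoms, the subject of the title. The trial also measures PANAS-X and the cognitive task on both sides of the drink (09:40 and 12:10), so it appears to look for an acute effect. The plan nowhere states that the acute effect on the other measures is taken to be nil.

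**Working it through.** **Timing, from Section 4.** Drink at 10:10.

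| Measure | Visit 1 value(s) | Relative to drink |
|---|---|---|
| Cognitive task, PANAS-X | 09:40 and 12:10 | first value 30 min before |
| Blood | 10:00 | 10 min before |
| BDI-II, PHQ-9 | 11:10 only | 60 min after |
| Heart rate variability | 11:25 only | 75 min after |

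Only the last two rows are affected.

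**The plan's own figures.** Section 1 gives N = 60, power 0.80, alpha 0.05 and partial eta squared 0.04. Then f = sqrt(0.04/0.96) = 0.204. For a two-group, two-measurement interaction, N = 60 is matched (power 0.81) if the within-person correlation is taken as 0.4. Section 1 does not state that correlation, so 60 is neither confirmed nor refuted, and this point does not rest on it. I use 60/2 = 30 per arm and, as an illustrative Visit 2 effect, 2f = 0.41 SD.

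**Model (assumed).** Normal data, SD 1 at both visits, correlation r. T is the Visit 2 effect and A the acute effect on the Visit 1 value, both signed so that benefit is positive. Expected group differences:

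- ANCOVA with the Visit 1 value: T - rA
- change score: T - A
- model without the Visit 1 value: T

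**One cell by hand: r = 0.6, A = 0.2, T = 0.**

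- Bias = -0.6 × 0.2 = -0.12 SD.
- SE = sqrt(1 - 0.36) × sqrt(4/60) × sqrt(1 + 0.2²/4) = 0.80 × 0.258 × 1.005 = 0.208.
- Ratio = 0.12/0.208 = 0.58. Two-sided rejection = Φ(0.58 - 1.96) + Φ(-0.58 - 1.96), about 8.9%.
- Simulation (3000 replicates, sex and diet also in the model) gives 8.5% and a mean estimate of -0.127.

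**Range of null rejection (simulation; nominal 5%).**

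| r | A = 0.1 | A = 0.2 | A = 0.3 |
|---|---|---|---|
| 0.4 | 5.3% | 6.3% | 7.2% |
| 0.6 | 6.3% | 8.5% | 12.6% |
| 0.8 | 7.8% | 16.5% | 31.3% |

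At A = 0 the rate is 4.6-5.2%, so there is no problem without an acute effect. The model without the Visit 1 value stays at 4.7-5.9% throughout.

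**With a real Visit 2 effect (T = 0.41, A = 0.2, r = 0.6).** Expected estimates are 0.41 - 0.12 = 0.29 (ANCOVA), 0.41 - 0.20 = 0.21 (change score) and 0.41 (no Visit 1 value). Power is 0.25, 0.14 and 0.34.

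**Could the trial detect it?** Hardly. A t test on the Visit 1 value has 7/12/21% power at shifts of 0.1/0.2/0.3 SD. Shapiro-Wilk on the residuals fails in 4.2-4.6% whether or not there is a shift. Rank ANCOVA with the same covariate does not repair it: 5.9/8.2/11.7% null rejection at r = 0.6.

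**Is dropping the Visit 1 value better?** Root mean squared error at r = 0.6, as sqrt(bias² + SE²):

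- A = 0.1: sqrt(0.06² + 0.207²) = 0.215
- A = 0.2: sqrt(0.12² + 0.208²) = 0.240
- A = 0.3: sqrt(0.18² + 0.209²) = 0.276
- without the Visit 1 value: sqrt(4/60) = 0.258

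Simulation agrees in ordering: 0.225 v 0.267 at A = 0.1 and 0.245 v 0.265 at A = 0.2. At shifts of 0.1 and 0.2 the biased ANCOVA also has the smaller error at r = 0.4 (0.250 v 0.268; 0.260 v 0.266) and r = 0.8 (0.177 v 0.265; 0.225 v 0.258). The order reverses at 0.3.

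**The case against.** The strongest reply is that the harm depends wholly on an acute effect that no section reports. The questionnaires and heart rate variability are taken once per visit, unlike PANAS-X and the cognitive task. The authors may therefore regard them as measures of the longer home-consumption phase, insensitive to one drink. That is a fair reading, and the 31.3% cell is an extreme one: its 0.3 SD shift is about three quarters of the 0.41 SD planning effect. What remains is that the plan does not state this assumption and, with 30 per arm, could barely test it.

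Second, screening assesses eligibility criteria that the document does not list, so a screening questionnaire score is not excluded. This stands. Naming such a score as baseline would settle the matter for that questionnaire.

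Third, omitting the Visit 1 value is not a clear improvement, since it has the larger error at shifts up to 0.2 SD. This also stands, and that model should not be imposed as the main one.

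A reader might also take the proviso in Section 5, which names no replacement for ANCOVA, as the serious fault. The figures do not support that. With an unaffected baseline and residual skewness of 0.5-1.4, an ordinary switch after a failed normality check keeps the error rate at 4.3-5.8%. It is a minor missing detail, separate from this point, and residual checks would not reveal the timing problem anyway.

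**Conclusion.** Read together, Sections 4 and 5 adjust the questionnaires and heart rate variability for a value taken 60 and 75 minutes after the randomised drink. That follows from the listed times and needs no assumption beyond taking the listed Visit 1 value as the baseline. The size of any bias, -rA, cannot be derived from the documents. In the illustration it is -0.12 SD with about 9% null rejection (r = 0.6, A = 0.2 SD), and it is zero if the drink has no acute effect.

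A reader might infer that the depression result will be biased or the analysis invalid. The documents do not support that, because they give neither an acute effect nor a correlation. What they support is that an unbiased result rests on an unstated assumption which a pre-drink baseline would make unnecessary. PANAS-X, the cognitive task and the blood measures are not affected.

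**What to change.** Reconcile Sections 4 and 5:

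1. At Visit 1, take the questionnaires and heart rate variability before the 10:10 drink, as already happens for PANAS-X, the cognitive task and blood. If a screening value exists, name it instead.
2. In Section 5, define baseline for every outcome as the last value recorded before the allocated drink.
3. For participants whose Visit 1 is over and who have no pre-drink value, report the analysis with and without the post-drink value, and state that the adjusted estimate assumes no acute effect. Choose the main model before unblinding and give the reason, since it trades bias against precision.

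Items 2 and 3 cost a few sentences. Item 1 lengthens the pre-drink session: the Visit 2 slots for these measures are 20 minutes (09:30-09:50) and 10 minutes (09:50-10:00), so about 30 minutes. It cannot be done retrospectively. The gain is worth having: at 0.41 SD, ANCOVA with an unaffected baseline has power 0.38/0.46/0.71 at correlations 0.4/0.6/0.8, against about 0.32-0.34 with no baseline.
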